9.4.2 ANALYSIS OF THE PRIMARY EFFICACY ENDPOINT(S)

The primary trial outcome will be the ketone (beta-hydroxybutyrate, BHB) levels 3 hours (T3) after consuming the study foods (Breakfast Bar or Fast Bar) and changes in BHB area under the curve (AUC) between 0 to 4 hours after consuming the study foods on day2.

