9 STATISTICAL CONSIDERATIONS

9.1 STATISTICAL HYPOTHESES

The primary trial outcome will be the ketone (beta-hydroxybutyrate, BHB) levels 3 hours (T3) after consuming the Fast and changes in BHB area under the curve (AUC) between 0 to 4 hours after consuming the study foods on day2.

We hypothesize that the breakfast bar group will show significant lower blood BHB level compared to the Fast Bar group.

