9.2 SAMPLE SIZE DETERMINATION

Sample-size estimation is based on two considerations:

1. Sample-size estimation is based on pilot studies assuming ketone (BHB) levels of 0.25 (SD: 0.19) and 0.16 (SD: 0.05) mM for the Fast Bar and the Breakfast groups, respectively. With t test (one-

tailed) of difference between two independent means, a total sample size of 62 will be necessary to achieve 80% power with an α error probability of 0.05. Sample size calculation was performed using the GPower v3.1.9.6 (Franz Faul, University Kiel, Germany; Actual power = 0.8164386; Actual α = 0.0291400).*

2. Sample-size estimation is based on Fisher's exact test (one tailed) for proportion difference between the breakfast and Fast Bar groups: food consumption will reduce blood ketone in 67% vs. 33% of the participants in the breakfast and Fast Bar groups, respectively. A total sample size of 64 will be necessary to achieve 80% power with an α error probability of 0.05. **

Based on prior experience in similar dietary intervention studies, we anticipate an approximate 10% dropout and/or data loss. 36 subjects per group will be enrolled. Sample size calculation was performed using the GPower v3.1.9.6 (Franz Faul, University Kiel, Germany; Actual power = 0.8164386; Actual α = 0.0291400). A fasting only group (32 subjects) will also be included for comparison. A total 108 subjects will be enrolled.

* **t tests** – Means: Difference between two independent means (two groups)

Analysis: A priori: Compute required sample size

Input:	Tail(s)	= One
	Effect size d	= 0.6478342
	α err prob	= 0.05
	Power (1- β err prob)	= 0.8
	Allocation ratio N2/N1	= 1
Output:	Noncentrality parameter δ	= 2.5505258
	Critical t	= 1.6706489
	Df	= 60
	Sample size group 1	= 31
	Sample size group 2	= 31
	Total sample size	= 62
	Actual power	= 0.8096862

** **Exact** – Proportions: Inequality, two independent groups (Fisher's exact test)

Options: Exact distribution

Analysis: A priori: Compute required sample size

Input:	Tail(s)	= One
	Proportion p1	= 0.67
	Proportion p2	= 0.33
	α err prob	= 0.05
	Power (1- β err prob)	= 0.8
	Allocation ratio N2/N1	= 1
Output:	Sample size group 1	= 32
	Sample size group 2	= 32
	Total sample size	= 64
	Actual power	= 0.8164386
	Actual α	= 0.0291400

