9.4 STATISTICAL ANALYSES

9.4.1 GENERAL APPROACH

Continuous trial outcome variables will be evaluated for normality; normalizing transformations or nonparametric statistics will be used as needed. All group comparisons on post-randomization efficacy outcomes will include randomized treatment (Fast Bar vs breakfast). A 1-sided level of significance set at $P<0.05$ will be used for the primary outcome; secondary and exploratory outcomes will not be adjusted for multiple hypothesis testing.

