9.4.3 ANALYSIS OF THE SECONDARY ENDPOINT(S)

The correlations of the time-dependent blood BHB levels between the groups (Fast Bar vs. Fasting and Fast Bar vs. Breakfast) will be carried out using Pearson correlation coefficient or Spearman's rank correlation analyses.

Separate analyses by treatment groups will test for difference in mean levels of continuous or prevalence of categorical outcomes.

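### The primary outcome joins T3 BHB and an undefined change in BHB AUC under one one-sided 0.05, with no rule saying whether either or both must succeed or in what order

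*Combined protocol and SAP*

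**What the plan says.** - **Primary outcome.** Section 9.4.2 consists of one sentence. It names BHB "levels 3 hours (T3) after consuming the study foods (Breakfast Bar or Fast Bar) and changes in BHB area under the curve (AUC", with a 0 to 4 hour window on day 2. It gives no test, order or success criterion. Section 9.1 pairs the same two measures, the second being "changes in BHB area under the curve (AUC) between 0 to 4 hours after consuming the study foods on day2".
- **Significance level.** This appears only in Section 9.4.1: a one-sided 0.05 "will be used for the primary outcome; secondary and exploratory outcomes will not be adjusted for multiple hypothesis testing".
- **Hypothesis.** Section 9.1: "We hypothesize that the breakfast bar group will show significant lower blood BHB level compared to the Fast Bar group". It gives no time point and does not mention AUC.
- **Sample size.** Section 9.2 has two bases. The t test rests on "assuming ketone (BHB) levels of 0.25 (SD: 0.19) and 0.16 (SD: 0.05) mM for the Fast Bar and the Breakfast groups", with no time point. The Fisher test rests on "food consumption will reduce blood ketone in 67% vs. 33% of the participants in the breakfast and Fast Bar groups", an outcome that Section 9.4.2 does not name. Enrolment follows: "we anticipate an approximate 10% dropout and/or data loss. 36 subjects per group will be enrolled".
- **Glucose.** The Synopsis and Section 3 list it as a primary endpoint beside BHB. Section 9 does not mention it. Only a general sentence in Section 9.4.3, that separate analyses "will test for difference in mean levels of continuous or prevalence of categorical outcomes", could take it in.

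**The concern.** A confirmatory trial needs a rule, fixed in advance, for when it counts as positive. Here two measures share one label and one alpha. Each possible reading has a consequence that the plan does not address:

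- If success on either measure is enough, two chances are taken at 5% each and the overall one-sided error exceeds 5%.
- If both are required, error is controlled, but the sample size was justified for a single comparison.

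The second measure also cannot be computed as written. A change in AUC could be the total area compared between arms, the area above T0, or a difference from another reference; Sections 1.3 and 8.1 also schedule a fasting reading on the morning of day 1. With neither the rule nor the variable fixed, both could be settled after the results are known.

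**Working it through.** **Inputs from the documents.** BHB 0.25 (SD 0.19) vs 0.16 (SD 0.05) mM; one-sided alpha 0.05; 31 per arm for the t test and 32 per arm for Fisher; about 10% loss; 36 enrolled per arm (all Section 9.2).

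**Inputs not in the documents.** The correlation r between T3 BHB and the AUC measure (range 0 to 0.95 used) and the standardized AUC effect (set equal to the BHB-level effect for illustration, then varied).

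**1. The plan's own figures.**
- d = (0.25 − 0.16) / √((0.19² + 0.05²)/2) = 0.09 / 0.1389 = 0.6478, as stated.
- Noncentral t, one-sided 0.05, 31 per arm: noncentrality 0.6478 × √(31/2) = 2.5505 and power 0.8097, as stated.
- The same test gives power 0.821 at 32 per arm and 0.859 at 36.
- Fisher, 67% vs 33%, 32 per arm: power 0.8164, as stated.
- Allowing for loss: 32/0.9 = 35.6, so 36; the t test alone gives 31/0.9 = 34.4, so 35. With 10% loss from 36, about 32 remain (36 × 0.9 = 32.4).

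The sample-size arithmetic is correct. The power is that of one test at one-sided 0.05.

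**2. If either measure may succeed.** Error = 0.05 + 0.05 − P(both reject under the null), with the last term from a bivariate normal with correlation r and cut-off 1.645.

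| r | P(both reject) | Error |
|---|---|---|
| 0 | 0.0025 | 9.75% |
| 0.3 | 0.0071 | 9.3% |
| 0.5 | 0.0122 | 8.8% |
| 0.8 | 0.0248 | 7.5% |
| 0.9 | 0.0319 | 6.8% |
| 0.95 | 0.0371 | 6.3% |

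The value at r = 0 is the upper end for non-negative correlation. T3 lies inside the AUC window, so a positive correlation is likely.

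**3. If both must succeed.** Error is at most 5%. Joint power is the bivariate normal probability at the probits of the two single-test powers. With d = 0.648 for both:

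| r | 32 per arm | 36 per arm |
|---|---|---|
| 0 | 0.67 | 0.74 |
| 0.5 | 0.72 | 0.77 |
| 0.8 | 0.75 | 0.80 |
| 0.95 | 0.79 | 0.83 |

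These are not bounds. At 32 per arm, over the same range of r, an AUC effect of d = 0.5 gives 0.52 to 0.63 and d = 0.8 gives 0.77 to 0.82.

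**4. Does the AUC definition matter?** Take five hourly readings with trapezoid weights 0.5, 1, 1, 1, 0.5, and a within-person correlation of 0.3 to 0.9 (compound symmetry or first-order autoregressive). With equal variances, T3 correlates 0.65 to 0.96 with total AUC, but from about 0.08 to less than 0.5 with AUC above T0. If the T0 SD is half the later SD, the correlation with AUC above T0 becomes 0.53 to 0.91. So the definition can change r a good deal, but the documents do not give the T0 variance that would fix its value.

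**The case against.** The best defence is the wording. Both sections speak of a single outcome and join the two measures with a conjunction; nothing suggests that one alone is enough. Read literally, both are required and the error rate is held. This stands in part: it may well be what the sponsor means, and it is why the point is a should-fix. But it is not written as a rule, and on that reading the power in Section 9.2 is not the power of the trial's success criterion.

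A reader might infer more than the documents support:

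- **That the trial runs above 5% error.** This holds only if either measure may succeed, and no section says so.
- **That the error is close to 9.75% because AUC above T0 is nearly unrelated to T3.** That needs equal variance at T0 and later, which no section supports. The two SDs in Section 9.2 differ almost fourfold between arms, so equal variance across feeding conditions is doubtful.
- **That the trial is underpowered at 0.67 to 0.79.** No AUC effect is stated, so this range only illustrates.
- **That glucose is a third unadjusted primary test.** The Synopsis and Section 3 give it that label, but Section 9 attaches no test to it. It is an inconsistency between sections, and no error figure follows.

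**Conclusion.** The point holds as a gap in the decision rule and in the definition of the AUC measure. Error above 5% (6.3% to 9.75% for assumed correlations of 0.95 down to 0) arises only if either measure may succeed. If both are required, the cost is in power: the stated 80% is for one comparison, and joint power would be about 0.67 to 0.79 at 32 evaluable per arm, or 0.74 to 0.83 at 36, if AUC had the same standardized effect. All these figures rest on a correlation, and the power figures also on an AUC effect, that the documents do not give. The sample-size calculations reproduce and need no correction. Should-fix.

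**What to change.** 1. **Sections 9.1 and 9.4.2: state the rule.** Test T3 BHB, Fast Bar vs breakfast, at one-sided 0.05, then AUC at one-sided 0.05 only if T3 is significant. T3 is the only level named as primary, so it is the closest match to the t-test sizing. If the sponsor means that both are required, say so and restate the power in Section 9.2 as joint power, with an assumed AUC effect and correlation.
2. **Define the AUC before data are seen.** For example, the trapezoidal area of BHB minus the T0 value over T0 to T4, in mM × h; or state that total AUC is meant.
3. **Section 9.2: confirm the time point of 0.25 vs 0.16 mM.** If it is T3, power for the first test is about 82% at 32 evaluable per arm and 86% at 36, so 36 enrolled per arm still suffices. If not, recheck the size.
4. **Separate and lesser: reconcile glucose.** Make it secondary throughout, or give it a hypothesis and a place in the test sequence.

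**Cost.** The sequence is a wording change, with no alpha split and no extra enrolment. Its downside is that a formal AUC claim depends on T3 succeeding. The both-required rule may cost more: with equal effects and r = 0, each test needs power √0.8 = 0.894 for 80% joint power, which takes 41 evaluable per arm. Keeping glucose primary would add a step to the sequence.

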9.4.3 ANALYSIS OF THE SECONDARY ENDPOINT(S)

The correlations of the time-dependent blood BHB levels between the groups (Fast Bar vs. Fasting and Fast Bar vs. Breakfast) will be carried out using Pearson correlation coefficient or Spearman's rank correlation analyses.

Separate analyses by treatment groups will test for difference in mean levels of continuous or prevalence of categorical outcomes.

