3 OBJECTIVES AND ENDPOINTS

The research questions to be addressed are:

1. What are the metabolic effects of consuming a Fast Bar™, as compared to consuming a typical breakfast, after an overnight fast?
2. Based on the observed metabolic effects, does consumption of a Fast Bar™ allow for maintenance of the fasting state?
3. Does consumption of a Fast Bar™ facilitate fasting by modulating subjective variables?

OBJECTIVES	ENDPOINTS	JUSTIFICATION FOR ENDPOINTS
Primary		
Physiological condition associated with fasting	
• Blood ketone (β-hydroxybutyrate, BHB) level• Blood glucose level	When hepatic glycogen stores are exhausted (after 12-24 hours of total fasting), the liver produces ketones (ketogenesis: acetoacetate (AA) and BHB) to provide an energy substrate for peripheral tissues.
Secondary		
Questionnaires	
• Food evaluation• Self-evaluation	The secondary objective is to assess the subjective variables

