4 STUDY DESIGN

4.1 OVERALL DESIGN

This is quantitative research with a randomized, single-blinded, controlled, parallel-arm design.

Total length of subject participation is 2 days.

The study will be carried out off-site (at participants' home).

After the explanation of the study and informed consent signature, eligible participants will be randomized to three groups.

1. Subjects in all groups will be asked to consume a standardized ready-to-eat dinner meal before 5 pm on day 1.
2. Breakfast Group: overnight fasting (approximately 15 hours), then consume a breakfast on day 2;
3. Fast Bar Group: overnight fasting (approximately 15 hours), then consume a Fast Bar™ on day 2.
4. Water-only fasting group: overnight fasting (approximately 19 hours);
5. Subject all groups will be asked not to consume any food or calorie-containing drinks other than the study foods till 2 pm on day 2.

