4.3 JUSTIFICATION FOR DOSE

Fasting leads to the mobilization of hepatic glycogen stores. When the glycogen stores are exhausted (after 12-24 hours of total fasting), the liver produces ketones (ketogenesis: acetoacetate (AA) and β -hydroxybutyrate (BHB) to provide an energy substrate for peripheral tissues. Consumption of food, depending on the composition of the food, i.e., the absolute levels and ratios of carbohydrate, protein and fat, may markedly affect the ketogenesis state. We hypothesis that the specially formulated Fast Bar™ will not significantly impact the overnight fasting-induced ketogenesis state.

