9.4.6 PLANNED INTERIM ANALYSES

An interim analysis will be carried out when 50% of the trial has been completed. Interim analysis will assess the accrual rates, basic characteristics of the study population, protocol adherence, and answer following questions:

1. Are the assumptions under which the original sample size was computed appropriate?
2. Is it likely that a relevant intervention difference will be demonstrated?

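### The only efficacy analysis that names the water-fast arm is a between-group correlation of BHB, which is blind to BHB level and cannot show whether the Fast Bar maintains the fasting state

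*Combined protocol and SAP*

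**What the plan says.** Section 3 lists three research questions. The second is: "Based on the observed metabolic effects, does consumption of a Fast Bar™ allow for maintenance of the fasting state". Section 4.3 adds the hypothesis that the bar "will not significantly impact the overnight fasting-induced ketogenesis state".

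Section 4.1 describes a "randomized, single-blinded, controlled, parallel-arm design" with three arms. Of the third arm, Section 9.2 says: "A fasting only group (32 subjects) will also be included for comparison". The hypothesis in 9.1, both sample-size calculations in 9.2, the general approach in 9.4.1 and the primary outcome in 9.4.2 all concern Fast Bar against breakfast.

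The fasting arm is named in an efficacy analysis only in 9.4.3: "The correlations of the time-dependent blood BHB levels between the groups (Fast Bar vs. Fasting and Fast Bar vs. Breakfast) will be carried out", with Pearson or Spearman coefficients. The next sentence reads: "Separate analyses by treatment groups will test for difference in mean levels of continuous or prevalence of categorical outcomes". It names no arm, endpoint or time point. The documents contain no equivalence or non-inferiority margin and no definition of a maintained fasting state.

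**The concern.** A correlation needs paired observations. In a parallel design no subject in one arm belongs with a subject in another, and 9.4.3 does not state the unit of analysis. The most natural reading is that the arm means at T0 to T4 are correlated, which leaves five points. Whatever pairing is chosen, Pearson is unchanged by a shift or a positive rescaling of either series, and Spearman by any increasing transformation. Neither can register that one arm has lower BHB than the other, which is the substance of question 2.

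The generic test of means does not fill the gap. Even if it is meant to cover the fasting arm, absence of significance without a margin is not evidence of maintenance. A high r or a non-significant test could therefore be reported as support for question 2 and for the Section 4.3 hypothesis while BHB was materially lower than under water fasting.

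**Working it through.** **Inputs.** From Section 9.2: pilot BHB 0.25 mM (SD 0.19) for Fast Bar and 0.16 mM (SD 0.05) for breakfast, a difference of 0.09 mM; 36 per group enrolled; 32 stated for the fasting arm. The total of 108 and the 1:1:1 allocation imply 36 for that arm too, so 32 to 36 per arm is used. No mean or SD is given for the fasting arm. I assume an SD from 0.139 mM, which is √[(0.19² + 0.05²)/2], to 0.19 mM.

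**The plan's own figures.** d = 0.09/0.1389 = 0.648. With 31 per arm and one-sided 0.05, power is 0.8097, as stated. Fisher's exact test with 32 per arm gives power 0.8164 and actual α 0.0291, as stated. 32/0.9 rounds up to 36. These figures are sound, but none concerns Fast Bar against fasting.

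**1. Blindness to level.** Take illustrative fasting means of 0.20, 0.25, 0.30, 0.36 and 0.42 mM at T0 to T4. A Fast Bar curve with the same T0 and half the rise is 0.20, 0.225, 0.25, 0.28 and 0.31. Pearson r = 1.000 and Spearman = 1.000, while T3 differs by 0.36 − 0.28 = 0.08 mM.

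**2. Five points.** The critical |r| at two-sided 0.05 is t/√(t² + 3) with t(0.975, 3) = 3.182, which is 0.878 whatever the BHB levels.

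**3. With sampling error.** Simulated arm means (32 per arm, assumed SD 0.19 mM, assumed within-person correlation 0.7):

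| True curves (mM, T0–T4) | Median r | 5th–95th percentile | r > 0.878 |
|---|---|---|---|
| Fasting 0.25, 0.30, 0.36, 0.43, 0.50; Fast Bar at half that level | 0.95 | 0.84 to 0.99 | 89% |
| Both 0.25, 0.26, 0.27, 0.28, 0.29 | 0.51 | −0.36 to 0.92 | 10% |
| Both flat at 0.25 | 0.00 | −0.80 to 0.81 | 3% |

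Halving BHB usually gives a significant r, and identical slow or flat curves usually do not.

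**4. What a test of means would show.** The 95% half-width is t × SD × √(2/n). The probability of a non-significant result for a true 0.09 mM deficit comes from the noncentral t (two-sided 0.05). The adjusted columns assume a T0–T3 correlation of 0.5, so SD is multiplied by √0.75 and df = 2n − 3.

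| SD | n per arm | Half-width | Non-significant | Half-width, adjusted | Non-significant, adjusted |
|---|---|---|---|---|---|
| 0.139 | 32 | 0.069 | 28% | 0.060 | 16% |
| 0.139 | 36 | 0.065 | 23% | 0.057 | 12% |
| 0.19 | 32 | 0.095 | 54% | 0.082 | 42% |
| 0.19 | 36 | 0.089 | 49% | 0.077 | 37% |

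**5. Power to claim maintenance.** This is the probability that the lower 95% limit exceeds minus the margin, with true difference 0 and no T0 adjustment. At an illustrative 0.09 mM margin it is 46% to 51% (SD 0.19) or 72% to 77% (SD 0.139). At 0.05 mM it is 18% to 20% or 29% to 33%.

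No AUC SD is given, so precision for AUC cannot be computed.

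**The case against.** The plan never says that the correlation is meant to answer question 2; it may only describe curve shape. The confirmatory comparison is with breakfast, and Section 4.2 frames the aim as a smaller and briefer departure from fasting than breakfast causes, which that comparison addresses. The generic sentence in 9.4.3 may already cover Fast Bar against fasting. The r = 1.000 example is an exact linear transform, so its result is built in. The SD range is assumed, and 0.139 draws on the breakfast arm, which is not in this contrast. Section 9.4.1 sets one-sided 0.05 for the primary outcome, whereas a 95% lower limit is one-sided 0.025. Glucose is a listed primary endpoint in the synopsis and Section 3, so calling it supportive may seem a downgrade.

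Some of this changes the size. At one-sided 0.05, non-significance falls to 14%–41% and power at the 0.09 mM margin rises to 59%–64% (SD 0.19) or 82%–86% (SD 0.139). At an assumed SD of 0.25 mM the unadjusted half-width would be 0.118 to 0.125 mM.

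None of it gives question 2 a valid analysis. The relative aim of 4.2 is question 1; question 2 is listed separately, and beating breakfast is compatible with BHB well below fasting. If the generic sentence does cover the fasting arm, it still lacks an endpoint and a margin. The simulation shows that the correlation's failure does not depend on an exact transform. Calling glucose supportive within this secondary contrast agrees with the BHB-only primary outcome in 9.1 and 9.4.2.

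**Conclusion.** The concern holds. As written, the correlation cannot show that the Fast Bar maintains the fasting state, and a low value would not refute it. That conclusion follows from the parallel design and the properties of the coefficients and does not depend on any assumed number. The sizes do: with SD 0.139 to 0.19 mM and 32 to 36 per arm, a test of means without a margin would miss a true deficit of 0.09 mM 23% to 54% of the time, or 12% to 42% with T0 adjustment at an assumed correlation of 0.5.

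The primary comparison with breakfast is unaffected. A stated research question, and the purpose of about a third of the randomised subjects, are left without a suitable specified analysis. This should be fixed. The fault is in the written analysis: the schedule of activities in Section 1.3 has BHB at T0 to T4 with no arm excluded.

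**What to change.** In 9.4.3, replace the correlation with the Fast Bar minus water-only fast difference in T3 BHB and in 0–4 h BHB AUC, each with a 95% confidence interval and adjusted for T0 BHB. Report glucose the same way as supportive. Claim maintenance only if the lower limit of the BHB difference lies above a margin that the sponsor fixes and justifies before any outcome data are examined. That includes the interim analysis in 9.4.6, which asks: "Is it likely that a relevant intervention difference will be demonstrated". If no margin can be justified, report the estimate and interval without that claim. Align the hypothesis in 4.3 with whichever course is taken. Because Section 8.1 times the samples from eating a bar, also state that T0 is the time origin in the fasting arm.

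The cost is protocol wording and one extra contrast, with no new subjects or samples. The sponsor must commit to a margin and accept limited power: unadjusted, 46% to 77% at an illustrative 0.09 mM and 18% to 33% at 0.05 mM across the assumed SDs. These margins show scale only and are not proposals.
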